### 3 INTRODUCTION

This SAP has been developed to supplement the statistical analyses described in the clinical study protocol final version dated 22 May 2013, notes to file 01 (09 Oct 2013) and 02 (10 Dec 2013).

This SAP describes the methodology and considerations of the planned analyses and a list of all the TFLs for this study. A detailed description of the planned TFLs will be provided in a separate TFL shells document. Any changes to the TFL shells numbering or to the title of the TFLs will not require an amendment to this SAP.

This SAP and any amendments will be finalized prior to the lock of the clinical database. Any changes to the analyses described in this document or additional analyses performed to supplement the planned analyses, will be described in the clinical study report (CSR).

The preparation of this SAP is based on the following documents:

- International Conference on Harmonisation (ICH) E9 guideline entitled, “Guidance for Industry: Statistical Principles for Clinical Trials” (**ICH Guideline E9, 1998**).
- ICH E3 guideline entitled, “Guidance for Industry: Structure and Content of Clinical Study Reports” (**ICH Guideline E3, 1995**).
- The Committee for Medicinal Products for Human Use (CHMP) Guideline on the Investigation of Bioequivalence (**CHMP, 2010**).
- The Appendix IV of the CHMP Guideline on the Investigation on Bioequivalence (**CHMP Appendix IV, 2011**).
- Food and Drug Administration (FDA) Guidance to Industry for Statistical Approaches to Establishing Bioequivalence (**FDA, 2001**).
- Electronic case report forms (eCRF) Final Version 4.0 dated 10 December 2013.
- Biostatistical Addendum – Subject Randomization List version 2.0 (16 April 2013).

#### 3.1 Revision History

Version	Date of Revision	Revision
3.0	23 April 2014	

• For a number of subjects the nicotine concentrations at <math>T_0</math> were higher than expected, therefore the statistical analyses were updated to accommodate this finding:

1) The primary analysis was updated to include all subjects irrespective of their <math>T_0</math>.

2) The originally planned analysis (SAP v1.0) became a supportive analysis (excluding subjects based on the concentrations their <math>T_0</math> with respect to their <math>C_{max}</math>).

• Clarification of the analysis of the Cotinine data that is specified in the protocol.

Version	Date of Revision	Revision
		

• Listing on the advise of risk of smoking will not be produced as data will not be available in the analysis data sets.

• Clarification that data collected at discharge visit will be presented at Day 4/Discharge.

• The document Revision History was added to the SAP.

2.0	18 December 2013	

• The SAP was updated to incorporate a number of minor changes across different document sections, including fixing of typos, re-wording and text format, TFL numbers and titles, and the specification of the following statistical analysis methods.

• Data handling methods and sensitivity analysis were expanded to address missing time data for <math>T_0</math> and PK assessment timepoints.

• A sensitivity analysis using bootstrap technique for the evaluation of the MCEQ domain scores was added.

1.0	23 August 2013	Original SAP

## 4 ABBREVIATIONS AND DEFINITION OF TERMS

The following abbreviations are used within this SAP.

%AUC extrap	Percentage of AUC that is due to extrapolation from $t_{last}$ to infinity
AE/SAE	Adverse Event/ Serious Adverse Event
ANOVA	Analysis of Variance
ATC	Anatomical Therapeutic and Chemical
AUC	Area under the curve
AUC (0-∞)	Area under the plasma concentration-time curve from start of product use extrapolated to infinite time
AUC (0-last)	Area under the plasma concentration-time curve from start of product use to the time of the last quantifiable concentration.
AUC (0-t')	Area under the plasma concentration-time curve from start of product use to the subject-specific $t'$
AUQ	Above the Upper limit of Quantification
BLQ	Below the Lower limit of Quantification
BMI	Body Mass Index
CC (s)	Conventional Cigarette(s)
CH	Cigarette Holder
CHMP	Committee for Medicinal Products for Human Use
CI	Confidence Interval
C last	The last quantifiable concentration
C max	Maximum observed plasma concentration.
CO	Carbon Monoxide
COHb	Carboxyhemoglobin
COT	Cotinine
CSR	Clinical Study Report
CTCAE	Common Terminology Criteria for Adverse Events and Common Toxicity Criteria
CV	Coefficient of Variation
CYP2A6	Cytochrome P450 2A6
DDE	WHO Drug Dictionary Enhanced
ECG	Electrocardiogram
eCRF	Electronic Case Report Form
EDC	Electronic data capture
FDA	Food and Drug Administration
FEV 1	Forced Expiratory Volume in 1 second
FTND	Fagerström Test for Nicotine Dependence
FVC	Forced Vital Capacity
HCOT	Trans-3'hydroxycotinine
HIV	Human Immunodeficiency Virus
ICF	Informed Consent Form
ICH	International Conference on Harmonisation

ISO	International Organization for Standardization
[REDACTED]	[REDACTED]
LLOQ	Lower Limit of Quantification
LS	Least Squares
mCC(s)	Menthol conventional cigarette(s)
MCEQ	Modified Cigarette Evaluation Questionnaire
MedDRA	Medical Dictionary for Regulatory Activities
MSE	Mean square error of the fitted model residual
NNS	Nicotine Nasal Spray
NR	No Result
PI	Principal Investigator
PK	Pharmacokinetic
PT	Preferred Term
QC	Quality Control
QSU-brief	Questionnaire of Smoking Urges Brief
QTcB	QT Interval Corrected using Bazett's Formula
QTcF	QT Interval Corrected using Fridericia's Formula
RBC	Red blood cells
REML	Restricted Maximum Likelihood
SAP	Statistical Analysis Plan
SD	Standard Deviation
SES	Socio-Economic Status
SOC	System Organ Class
SOP	Standard Operating Procedure
$t'$	The subject-specific time of maximum nicotine concentration following single use of the mCC or NNS product, between the THS 2.2 Menthol and mCC, as well as the THS 2.2 Menthol and NNS
$T_0$	Time of first product use at single use day
$t_{1/2}$	Terminal elimination half-life
TFL	Tables, Figures, and Listings
THS	Tobacco Heating System
$t_{last}$	Time of last quantifiable concentration
$t_{max}$	Time of maximum observed plasma concentration
ULOQ	Upper Limit of Quantification
VAS	Visual Analogue Scale
WBC	White blood cells
WHO	World Health Organisation
$\lambda_z$	Terminal elimination rate constant, estimated by linear regression analysis of the natural log-transformed concentration-time data

The following special terms are used in this SAP:

CC and mCC	The term ‘conventional cigarette’ refers to manufactured and commercially available cigarettes and excludes hand-rolled cigarettes, cigars, pipes, bidis, and other nicotine-containing products. Menthol CC are designated “mCC”.
Enrolment	On Day -1 for eligible subjects (all applicable inclusion and exclusion criteria have been satisfactorily met) and the subjects is willing and ready to use both the THS 2.2 Menthol and NNS (the test of both THS 2.2 Menthol and NNS are the last assessments prior to enrolment)
First product use within each Single Use day	Start of product use: 

• THS 2.2 Menthol is defined as the time of the first puff.

• mCC corresponds to the lighting of the mCC

• NNS is the time of the spray in the first nostril

Randomization	Assignment to product on Day 0 using an [REDACTED]
Safety follow-up	After the discharge, a 7-day safety follow-up will be done for the recording of spontaneously reported new AEs/SAEs and the active follow-up of ongoing AEs/SAEs by the site. In general any AE will be followed up until resolved, stabilized i.e. no worsening of the event or a plausible explanation for the event has been found.
Screening failure	Subjects who do not enroll into the study
Tobacco Heating System 2.2 Menthol (THS 2.2 Menthol)	THS 2.2 Menthol is composed of the following components: Tobacco Stick, Holder, Charger, a Cleaning Tool, a main power supply, and a USB cable.

## 5 STUDY OBJECTIVES AND ENDPOINTS

The endpoints specify randomization groups (Group-1 or Group-2) that are being analyzed for the objective when it is not applied to both (the randomization groups are defined in Table 1 of Section 6.1).

### 5.1 Primary Objective and Endpoints

1. To evaluate the rate and the amount of nicotine absorbed (as assessed by maximum plasma concentration [ $C_{max}$ ] and area under the concentration-time curve [AUC] from start of product use to time of last quantifiable concentration [ $AUC_{(0-last)}$ ]) from THS 2.2 Menthol relative to menthol conventional cigarettes (mCC), following single use of THS 2.2 Menthol and mCC.

Endpoints:

- $C_{max}$  [mCC and THS 2.2 Menthol, Group-1]
- $AUC_{(0-last)}$  [mCC and THS 2.2 Menthol, Group-1]

### 5.2 Secondary Objectives and Endpoints

1. To determine if  $C_{max}$  and  $AUC_{(0-last)}$  of the THS 2.2 Menthol are higher relative to nicotine nasal spray (NNS) following single use of the THS 2.2 Menthol and NNS.

Endpoints:

- $C_{max}$  [NNS and THS 2.2 Menthol, Group-2]
- $AUC_{(0-last)}$  [NNS and THS 2.2 Menthol, Group-2]

2. To evaluate the difference on nicotine pharmacokinetic (PK) absorption parameters (AUC from start of product use extrapolated to time of last quantifiable concentration to infinity [ $AUC_{(0-\infty)}$ ] and partial AUC, where  $t'$  is the subject-specific time of maximum nicotine concentration following single use of the mCC or NNS product [ $AUC_{(0-t')}$ ]) between the THS 2.2 Menthol and mCC, as well as the THS 2.2 Menthol and NNS.

Endpoints:

- $AUC_{(0-\infty)}$ .
- Partial  $AUC_{(0-t')}$ .

3. To evaluate the time to the maximum concentration ( $t_{max}$ ) of nicotine for the THS 2.2 Menthol as compared to mCC and to determine if the  $t_{max}$  for THS 2.2 Menthol is shorter as compared to NNS.

Endpoint:

- $t_{max}$ .

4. To describe the terminal half-life ( $t_{1/2}$ ) of nicotine for the THS 2.2 Menthol, mCC, and NNS.

Endpoint:

- $t_{1/2}$ .

5. To describe the differences on urge-to-smoke over time between the THS 2.2 Menthol and mCC, as well as between the THS 2.2 Menthol and NNS.

Endpoints:

Urge-to-smoke as measured with the Questionnaire of Smoking Urges brief (QSU-brief) (Cox et al, 2001).

- Total score.
- Factor-1.
- Factor-2.

6. To describe product evaluation in the THS 2.2 Menthol and mCC users.

Endpoints:

Product evaluation as measured with the Modified Cigarette Evaluation Questionnaire (MCEQ) (Cappelleri et al, 2007) [mCC and THS 2.2 Menthol, in Group-1].

- Smoking Satisfaction subscale.
- Enjoyment of Respiratory Tract Sensation subscale.
- Psychological Reward subscale.
- Aversion subscale.
- Craving Reduction subscale.

7. To describe the levels of carbon monoxide (CO) exposure for the THS 2.2 Menthol, as compared to mCC and NNS users.

Endpoints:

- Levels of exhaled CO.
- Carboxyhemoglobin (COHb) in blood.

8. To describe the plasma levels of cotinine in the THS 2.2 Menthol, mCC, and NNS.

Endpoints:

- Levels of cotinine in plasma.

9. To monitor the safety during the study.

Endpoints:

- Incidence of adverse events (AEs)/serious adverse events (SAEs) and device events, including THS 2.2 Menthol malfunction/misuse.
- Respiratory symptoms: cough assessment by visual analogue and Likert scales and one open question.

- Vital signs (systolic and diastolic blood pressure, pulse rate, respiratory rate).
- Spirometry.
- Electrocardiogram (ECG).
- Clinical chemistry, hematology, and urine analysis safety panel.
- Physical examination.
- Concomitant medication.

### 5.3 Additional Endpoints

The following additional assessments will be made:

- Serology for human immunodeficiency virus (HIV) 1/2 and Hepatitis B and C.
- Urine pregnancy test (females only), urine cotinine test, urine drug screen.
- Alcohol breath test.
- Chest X-ray.
- Socio-economic status questionnaire (**King et al., 2011**).
- Nicotine dependence to be assessed with the Fagerström Test for Nicotine Dependence (FTND) revised version (**Fagerström et al, 2012**).
- Cytochrome P450 2A6 (CYP2A6) activity (nicotine metabolic molar ratio) in plasma.

### 5.4 Study Hypotheses And Evaluation Criteria

#### 5.4.1 Hypotheses

Given that the primary objective of this study is to determine the point estimate and precision of the nicotine relative bioavailability (ratio of THS 2.2 Menthol:mCC) for  $C_{max}$  and  $AUC_{(0-last)}$ , there is no statistical hypothesis to be tested for the primary objective.

For the secondary objectives the following hypotheses will be examined for THS 2.2 Menthol versus NNS analysis:

The hypotheses to be tested for the secondary objectives are:

- The geometric mean  $C_{max}$  in THS 2.2 Menthol is higher relative to NNS.
- The  $AUC_{(0-last)}$  in THS 2.2 Menthol is larger relative to NNS.
- The median  $t_{max}$  in THS 2.2 Menthol is shorter than in NNS.

#### 5.4.2 Evaluation Criteria

The study will be considered successful if the 95% confidence intervals (CI) of the THS 2.2 Menthol:mCC ratio for the nicotine  $C_{max}$  and  $AUC_{(0-last)}$  are estimated with a precision of  $\pm 20\%$ .

## 6 INVESTIGATIONAL PLAN

### 6.1 Study Design

This is a randomized, controlled, 2-period, 4-sequence, single use crossover study. An incomplete block design has been adopted, where each subject will receive two of the three products (Figure 1):

- THS 2.2 Menthol.
- mCC.
- NNS.

Nicotrol®NS 10 mg/mL is the NNS brand adopted in this study, and mCC brands allowed are reported in a note to file (No.2, 10 Dec 2013).

In total, 62 eligible, healthy smoking subjects will be randomized into one of the 4 sequences in Table 1:

**Table 1 Definition of Randomization Groups and Sequences**

Group	Allocation Ratio	Sequence	Sample Size
Group-1 = THS 2.2 Menthol vs. mCC	2:2	1. THS 2.2 Menthol then mCC 2. mCC then THS 2.2 Menthol	22 22
Group-2 = THS 2.2 Menthol vs. NNS	1:1	3. THS 2.2 Menthol then NNS 4. NNS then THS 2.2 Menthol	9 9

A Screening Visit will be conducted within 4 weeks prior to Admission to the investigational site (Day -29 to Day -2). A demonstration of the THS 2.2 Menthol product and the NNS will also be done by the site staff during the screening visit. Subjects will be admitted to the clinic on Day -1 (Admission). On Day -1, as the last procedure of the eligibility assessments on that day, all subjects will undergo a product test prior to enrolment, first THS 2.2 Menthol (using up to three Menthol Tobacco Sticks) and subsequently the NNS (1 spray of 0.5 mg per nostril as per label). In female subjects, the urine pregnancy test must be negative before the product test is performed with either THS 2.2 Menthol or NNS. After all inclusion and exclusion criteria have been met, only subjects willing and ready to use both the THS 2.2 Menthol and NNS products can be enrolled. Screening procedures do not necessarily have to be conducted on the same day.

Subjects are enrolled on Day -1, but not randomized until the Day 0 washout, therefore it is possible to have enrolled subjects who do not get randomized.

[figure not shown]
Subjects will be discharged from the investigational site in the morning of Day 4 after all safety examinations of the Day of Discharge have been conducted. After Discharge,

subjects will enter into a 7-day safety follow-up starting to capture spontaneously reported new AEs/SAEs and for active follow-up of ongoing AEs/SAEs. Any AE will in general be followed up until resolved, stabilized i.e., no worsening of the event, or until a plausible explanation for the event has been found.

The confinement consists of 2 periods (Period 1, Period 2) with each period consisting of at least 24-hour nicotine wash-out (nicotine abstinence) and 1 day of single product use.

### Figure 1. Study Flowchart

- Cross over with incomplete block design, 4 sequences
- 62 smokers to be randomized

THS: Tobacco Heating System; mCC: menthol conventional cigarette(s); NNS: nicotine nasal spray

#### 6.1.1 Timing of Confinement Period

The 6 day confinement period consists of:

- The Admission Day from admission on site until 06:30 AM on Day 0.
- The first washout period: from 06:30 AM on Day 0 until the time of first product use ( $T_0$ ) in the time window 6:00 AM-9:00 AM of Day 1.
- The first product exposure period (1 day): starting from  $T_0$  on Day 1, ending 24 hours after  $T_0$ .
- The second washout period: from the end of the first product exposure (24 hours after  $T_0$  on Day 1) on Day 2 until the time of product use in the time window 6:00 AM-9:00 AM on Day 3.
- The second product exposure period (1 day): starting from  $T_0$  on Day 3, ending 24 hours after  $T_0$ .

- The discharge procedures from 24 hours after T0 of the second product use until the time of discharge on Day 4.

## 6.2 Selection of Study Population

### 6.2.1 Inclusion Criteria

A total of 62 smoking, healthy adult subjects, meeting the following inclusion criteria will be randomized on to the study:

1. Subject has signed the informed consent form (ICF) and is able to understand the information provided in the subject information sheet and ICF.
2. Subject is aged from 22 to 65 years (inclusive).
3. Smoking, healthy subject as judged by the Investigator based on all available assessments in the Screening period / day of Admission.
4. Subject smokes at least 10 commercially available mCCs per day for the last 4 weeks. Furthermore, the subject has been smoking for at least the last 3 consecutive years.
5. The subject does not plan to quit smoking in the next 3 months.
6. The subject is ready to accept interruptions of smoking for up to 4 days.
7. The subject is ready to accept using both the THS 2.2 Menthol and the NNS products.

### 6.2.2 Exclusion Criteria

The exclusion criteria are:

1. As per Investigator judgment, the subject cannot participate in the study for any reason.
2. A subject who is legally incompetent, physically or mentally incapable of giving consent.
3. The subject has medical condition requiring smoking cessation, or clinically relevant diseases in the judgment of the Investigator.
4. The subject has a body mass index (BMI)  $<18.5$  or  $\geq 35.0 \text{ kg/m}^2$ .
5. As per Investigator judgment, the subject has medical conditions which require or will require in the course of the study a medical intervention which may interfere with the study participation and/or study results.
6. The subject has used nicotine-containing products other than commercially available mCC (either tobacco-based products or nicotine-replacement therapy) as well as electronic cigarettes and similar devices, within 4 weeks prior to assessment.
7. The subject has received medication within 14 days or within 5 half-lives of the drug prior to the Admission Day that has an impact on CYP2A6 activity.
8. In case the subject received any medication (prescribed or over the counter) within 14 days prior to Screening or prior to the Admission Day (Day -1) it will be decided at the discretion of the Investigator if these can potentially interfere with the study objectives and subject's safety.

9. The subject has a positive alcohol test and/or the subject has a history of alcohol abuse that could interfere with subject's participation in the study.
10. The subject has a positive urine drug test.
11. Positive serology test for HIV 1/2, Hepatitis B or Hepatitis C.
12. Donation or receipt of whole blood or blood products within 3 months prior to Admission.
13. The subject is a former or current employee of the tobacco industry or of their first-degree relatives (parent, sibling or child).
14. The subject is an employee of the investigational site or any other parties involved in the study or of their first-degree relatives (parent, sibling or child).
15. The subject has participated in a clinical study within 3 months prior to the Screening Visit.
16. The subject has previously participated in the same study at a different time (i.e., each subject can be included in the study population only once).
17. For women only: Subject is pregnant (does not have negative pregnancy tests at Screening and at Admission) or is breast feeding.
18. For women only: Subject does not agree to use an acceptable method of effective contraception.\*

\* Intrauterine device, intrauterine system, barrier methods of contraception (condoms, occlusive caps) with spermicidal foam/gel/film/suppository, hormonal contraception containing progesterone only, vasectomized partner(s), or true abstinence (periodic abstinence and withdrawal are not effective methods) from Screening until the end of the safety follow-up period. Hormonal contraception with estrogen containing products is NOT allowed in this study.

## 6.3 Product Allocation and Blinding

### 6.3.1 Methods of Assigning Subjects to Treatment Sequences

Randomization will be conducted through the [REDACTED]

Subjects will be randomized to either Group-1 (sequences 1 and 2) or to Group-2 (sequences 3 and 4). Each stratum: sex (male and female) and mCC nicotine level at Admission (ISO nicotine level  $\leq$ 1 mg and  $>$ 1 mg) will have a quota applied to ensure they represent at least 40% of the total study population. See Table 1.

To accomplish the above, the subject randomization list will contain randomization records for the 2 groups. A blocked randomization will be used. Subjects will be assigned to the next available sequence providing the quotas have not been met. Block size and other randomization details are available in the randomization plan.

The randomization scheme will be generated by the statistical division within [REDACTED] and none of the study team for this study, including study sponsor, [REDACTED] and Principal Investigator (PI) or the study subjects will be exposed to the live randomization codes prior to randomization.

### 6.3.2 Blinding

This is an open-label study; therefore, the subjects and PI will be unblinded to subject's sequence and product assignment after randomization. However, there will be a limited degree of blinding during the conduct of the study including the data review and data analysis process. In particular, PMI and [REDACTED] personnel will be blinded to the randomized sequence as summarized in Table 2.

**Table 2: Blinding Scheme**

Blinded Study Personnel	End of Blinding Period
PMI and [REDACTED] study statisticians	After the SAP finalization or database lock  , whichever comes last.
PMI study data managers	After the finalization of PMI blind database review  .
PMI safety and clinical scientist	After the finalization of PMI blind database review  . Can be actively un-blinded before that time point in case of the occurrence of any safety question, when appropriate.

 A [REDACTED] PK expert will perform an unblinded data review of PK data and will flag any anomalous data for the pre-analysis blinded data review conducted by PMI and [REDACTED]

 As part of the PMI Quality Control (QC) activity, data listings will be reviewed by [REDACTED] and PMI before database lock, with no access to the randomization sequence information. Full details will be available in the data review plan.

Any PMI and [REDACTED] personnel who are not listed in the above table will be unblinded by default.

Unblinding information will not be shared with the blinded study team without a dummy randomization or masking in place, until the end of the blinding period (see Table 2). PMI will receive blinded data for the pre-analysis data review as planned in the data review plan.

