#### 7.1.4 Anomalous Values

If a concentration value is considered to be anomalous due to being inconsistent with the expected PK profile it will be flagged in the listings and will be reviewed for inclusion in the analysis during the pre-analysis data review.

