## 8 SAMPLE SIZE JUSTIFICATION

A total of 62 smokers will be randomized. This sample size is the sum of the sample size requirements for the THS 2.2 Menthol:mCC comparison and the THS 2.2 Menthol:NNS comparison (as described in detail below).

A total of 44 subjects are needed to estimate the mean  $C_{max}$  parameter ratio between THS 2.2 Menthol and mCC with a 90% probability of obtaining a margin of error (95% CI) of at most  $\pm 20\%$ , assuming that THS 2.2 Menthol have a nicotine PK profile similar to mCC ( $C_{max}$  ratio equal to 1.00) and a 10% dropout rate.

A total of 18 subjects are needed to estimate the mean  $C_{max}$  parameter ratio between THS 2.2 Menthol and NNS with a precision allowing for the lower bound of the 95% CI exceeding 1.00, with 90% power and assuming a 10% dropout rate. The anticipated geometrical  $C_{max}$  ratio between THS 2.2 Menthol and NNS is 1.55, based on data reported by **Gourlay and Benowitz, 1997**, and **Johansson et al., 1991**.

The estimates for the within-subject CV for nicotine  $C_{max}$  (36%) and  $AUC_{(0\text{-last})}$  (21%) are based on the data collected in the ZRHX-PK-02 clinical study (ClinicalTrials.gov, number NCT01780688) comparing the nicotine PK profiles of Tobacco Heating System 2.1, the predecessor of THS 2.2 (non-menthol) and CC. In the absence of data comparing THS 2.2 Menthol and NNS, the same CVs were assumed for the calculation of the sample size related to the THS 2.2 Menthol:NNS comparison.

Sample size calculations were conducted using SAS® version 9.2 for the 95% CI of the mean differences between paired observations (proc power onesamplemeans) in the natural log scale (**Senn, 2002**). The SAS® implementation of the method published by **Beal, 1989** was adopted to estimate the probability of obtaining at most the target confidence interval of  $\pm 20\%$ .

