## 12.4 Final Analyses

Final analyses for this study will be performed only after database lock. A pre-analysis data review meeting will be held prior to database lock and completion of the final analyses. In addition, no database may be locked, randomization code unblinded, or analyses completed until the final version of this SAP has been approved.

Any post-hoc, additional exploratory analyses completed to support planned study analyses, which were not identified in this SAP, will be documented and reported as applicable. Any results from these unplanned analyses will also be clearly identified in the text of the CSR.

The list of all tables, figures and listings to be presented are included in the relevant sections of the SAP.

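### SAP 7.1.4 allows concentrations to be left out of the primary analysis for not fitting the expected profile, with no documented fault required, and an unblinded PK expert flags them

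*SAP*

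**What the plan says.** Footnote 1 to SAP Table 2 (section 6.3.2) states that a "PK expert will perform an unblinded data review of PK data and will flag any anomalous data for the pre-analysis blinded data review". SAP 7.1.4 gives the standard: "If a concentration value is considered to be anomalous due to being inconsistent with the expected PK profile it will be flagged in the listings". Such a value "will be reviewed for inclusion in the analysis during the pre-analysis data review". It sets no numeric rule and does not require a fault in sampling, labelling or assay. SAP 12.4 fixes the timing: "A pre-analysis data review meeting will be held prior to database lock and completion of the final analyses".

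The criterion that these values feed is in SAP 5.4.2: "The study will be considered successful if the 95% confidence intervals (CI) of the THS 2.2 Menthol:mCC ratio" for Cmax and AUC(0-last) are estimated to within ±20%. SAP 5.4.1 adds that "there is no statistical hypothesis to be tested for the primary objective". SAP 11.6.1 restricts the primary model to subjects evaluable on both products.

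The PK sensitivity analyses in SAP 11.6.3 deal with pre-use concentrations above 5% of Cmax, 20% or more missing parameters, and imputed seconds. None repeats the primary analysis with flagged and excluded concentrations put back. Exclusions are listed (SAP 11.2 and 11.6.3). Protocol 12.5.1 has no rule for anomalous values, and SAP section 9 does not name this one as a change.

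**The concern.** Two separate issues meet here.

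The first is outcome-based exclusion. Cmax is a single observed maximum, so removing a flagged peak can only lower it or make it unavailable. If the values removed are the ones that make a subject's two products disagree, the residual variance falls and the CI narrows. A narrow CI is what the trial counts as success, and the reported interval would no longer have 95% coverage.

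The second is who flags. Someone who knows the product may hold a different expected profile for THS 2.2 Menthol than for mCC, and may flag similar peaks differently. That could move the ratio itself.

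Elsewhere the SAP is more objective. Half-life needs at least 3 points, 1.5 half-lives and an adjusted R² of 0.7. A value below the LLOQ in mid-profile is queried and, if confirmed, kept by imputation. Section 7.1.4 relies on judgement alone.

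**Working it through.** **Inputs from the documents.** Within-subject CV 36% for Cmax and 21% for AUC(0-last); 44 subjects in Group-1; 10% dropout; a design "with a 90% probability of obtaining a margin of error (95% CI) of at most" ±20% (SAP section 8).

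**Assumptions made here.** CVs of 40% and 45%, and the number and kind of exclusions. The documents give none of these.

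**Step 1: reproduce the plan's figure.**
- SD of a within-subject log difference = √(2·ln(1 + CV²)) = √(2·ln 1.1296) = 0.494.
- Limit on the log half-width: h = ln 1.2 = 0.182.
- P(half-width ≤ h) = P(χ²_df ≤ df·n·h² / (t²·SD²)).
- n = 40, df = 39, t = 2.023: the bound is 52.0 and the probability 0.920 (0.917 with the crossover model's 38 df). At n = 39 it is 0.897.
- So 40 evaluable pairs are needed. 40 × 1.1 = 44, the stated number; 40/0.9 = 44.4 would round up to 45.
- Other readings of ±20% do not lead to 44: h = −ln 0.8 needs 29 evaluable pairs, h = 0.20 needs 34.

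**Step 2: drop the most discordant pairs.** Simulate 40 normal log differences, drop the k furthest from the median, set m = 40 − k, and compare t(0.975, m − 2)·s/√m with ln 1.2.

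| CV | k = 0 | k = 1 | k = 2 |
|---|---|---|---|
| 36% (planned) | 0.92 | 0.97 | 0.99 |
| 40% (assumed) | 0.68 | 0.84 | 0.91 |
| 45% (assumed) | 0.32 | 0.51 | 0.65–0.66 |

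True coverage of the nominal 95% CI: 0.95, then about 0.91–0.92 for k = 1 and 0.88–0.89 for k = 2. Coverage does not depend on the CV.

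**Step 3: keep the pair but soften it.** Moving the 1 or 2 most discordant differences halfway back gives 0.98 or 0.99 at CV 36%, and 0.85 or 0.93 at CV 40%. The result is therefore not peculiar to losing whole subjects.

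**Step 4: lose pairs at random.** At CV 36%, losing 1 or 2 random pairs lowers the probability from 0.92 to 0.89 or 0.87. The gain needs the excluded values to be the discordant ones.

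**Step 5: AUC(0-last).** At CV 21% the SD is 0.294, and 40 pairs meet the criterion with probability about 1.00 with or without exclusions.

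No step uses product labels. The figures measure exclusion under 7.1.4 and say nothing about the effect of unblinding.

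**The case against.** A reader might infer that an unblinded expert decides what is excluded. The SAP does not say that. The expert flags, a blinded review before lock decides, and exclusions are listed. Nor does it say that the meeting sees only the expert's flags: footnote 2 to Table 2 has listings reviewed without sequence information, with details in a data review plan that is not available here. These safeguards are real. They are partial, because flags raised with knowledge of product go into that meeting and no retained-data analysis shows what the exclusions did.

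A reader might also blame unblinding for the narrower CI. That is wrong: masked removal of the same values narrows it equally.

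A third tempting reading is that one or two exclusions turn a likely failure into a likely success. Only the assumed CV of 45% with two exclusions fits that (0.32 to about 0.65). At the planned CV success is already likely, and at 40% the start is 0.68.

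The proxy is also severe. Section 7.1.4 concerns single concentrations that break a profile, whereas the simulation picks the worst pairs. A smooth profile with a high peak need not be flagged, and removing a non-peak value leaves Cmax unchanged. Finally, there is no primary hypothesis, and SAP version 3.0 moved towards retention by including all subjects whatever their pre-use concentration. All of this limits the size of the problem. It does not supply a rule for 7.1.4.

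**Conclusion.** The point stands as a weakness in the rule. The documents show no misuse. Section 7.1.4 permits exclusion from the primary analysis for poor fit to an expected profile, without a documented fault. If the 1 or 2 most discordant of 40 pairs went, the chance of meeting the Cmax criterion would rise from 0.92 to 0.97 or 0.99 at CV 36%, and from about 0.68 to 0.84 or 0.91 at an assumed 40%, with true coverage near 0.91 or 0.88–0.89. These are upper-end figures, because the proxy picks the most discordant pairs. Random losses and non-peak exclusions do not produce the gain. Success on AUC(0-last) is essentially unaffected.

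Unblinded flagging is a separate and unquantified risk: product-dependent selection could shift the THS 2.2 Menthol:mCC ratio, but the documents give no basis for sizing it.

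**What to change.** In SAP 7.1.4, keep all quantifiable concentrations in the primary analysis unless a sampling, labelling or assay error is documented. Report exclusion of other flagged values only as a sensitivity analysis, and add it to 11.6.3.

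In SAP 6.3.2, have the PK expert flag with product and sequence masked, using the dummy randomization or masking that the section already mentions. Period may stay visible so that pre-dose carry-over can be judged. Parameters that need product identity, such as AUC(0-t'), can be derived after flagging.

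The cost is SAP wording, one sensitivity analysis and a set of masked listings. There is a small downside: a spurious value with no documented cause would stay in the primary analysis.
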